Over the course of this procedure, subjects will be asked to report various aspects of their experience – this will include responding to questions regarding their perceived control over their brain activity.

- i. In-Magnet Assessment 1: MPRAGE, Resting State, Initial Control Runs, and Localizer. If time allows, DTI data will also be collected.

During the first in-magnet assessment, a high resolution structural image will be collected using an MPRAGE sequence. Functional resting state data will be collected, as well as four control runs. During the resting state sessions spontaneous pupil dilation will be measured using a Eyelink 1000 system. As seen in Figure 2, control runs involve a resting period, exposure to a provocative audio clip, a period of down-regulation where participants try to bring down their amygdala activity, and a final resting period. In order to minimize anticipation and rumination regarding the upcoming or preceding stressor, resting periods are separated from the provocative audio clip and subsequent period of down-regulation by a 1-back memory task (seen in Figure 2 as “1-bk”). These memory tasks provide a cognitively-engaging distraction for the subject, preventing anticipatory and spill-over amygdala activity during resting periods and allowing for a more valid baseline to be established.

Rest	1-bk	Prov audio clip	Down-regulate	1-bk	Rest
60s	30s	60s	60s	30s	60s

Figure 2: Schematic illustration of a control task run. Control assessed based on activity in the target region of the amygdala in the down-regulate blocks (relative to rest)

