Three localizer runs will also be performed during this session. As seen in Figure 3, the localizer runs will involve a resting period, exposure to a provocative audio clip, and a final resting period. As in the control run, to ensure that resting periods are not affected by the symptom provocation, subjects will perform a 1-back working memory task between the rest periods and the provocative audio clips. In order to identify the part of the amygdala involved in trauma-related anxiety, activation during the trauma exposure will be compared to activity during the resting periods. The area of the amygdala located during this session will be used as the target for the brain activity that will be shown to subjects in future NF runs. As such, we must be able to identify adequate activation in the amygdala for NF to be possible – if no such activation can be identified, the subject will no longer be eligible for continuation of the study.

Rest	1-bk	Prov audio clip	1-bk	Rest
80s	40s	60s	40s	80s

Figure 3: Illustration of a localizer run. Activity will be contrasted between provocation and rest blocks to identify region of peak amygdala activity.

- ii. Randomization

All subjects who remain eligible following the localizer will be randomized to receive either NF or sham feedback, subject to the restriction that there must always be at least as many subjects in the NF group as in the sham group. We will not explicitly describe the sham feedback procedure to subjects – rather, all subjects will be told that they will be randomly assigned to receive either an experimental intervention (that we hope will help symptoms, but that has not yet been demonstrated to be effective) or a control intervention (that we do not believe can help symptoms). Subject will be blind to their condition until study completion, at which point we will tell them which intervention they received. At that point, those who received the control intervention (sham) will be given the option of trying the experimental intervention (NF).

It is important to note that all clinical assessments performed after randomization are carried out by a clinical psychologist who is blind to subject assignment.

iii. Neurofeedback and Sham Feedback

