- iv. *Control task activation analyses:* Control over the amygdala target region will be computed by running voxel-wise regression analyses separately for the two categories of traumas – trained (traumas with which the subject engaged in NF) and untrained (traumas that the subject was not exposed to during NF). Four regression analyses will be run per subject – one per category from each of the two assessment sessions. Regressors will be defined for the task periods using boxcar functions convolved with a canonical hemodynamic response function. Three regressors will be used, corresponding to the provocation block, the down-regulate blocks of interest, and the 1-back periods (the lattermost being included to remove the effects of the 1-back periods and make contrasts relative to the rest blocks). Resulting maps of beta values for the regulate and provocation blocks will be transformed to a common space (see above section I.b.) and masked with the target region (also transformed to common space). Average value in the target region will be computed separately from beta maps for the provocation and down-regulate blocks to yield estimates of activation in the amygdala in each condition of each assessment session for the trained and untrained trauma memories. **All analyses outlined in the following sections will use data from the regulation blocks of the untrained traumas unless otherwise noted.**
- v. *Resting state analyses:* In addition to the offline neuroimaging data analyses described above in section I., resting state data collected during each In-Magnet Assessment will be low-pass filtered (0.1 Hz), motion parameters, and the average time-courses of the ventricles and white matter will be regressed from the data. Seed maps of connectivity to the amygdala will then be computed. First, the time-courses of voxels in the target area will be averaged to yield a reference seed region time-course. This time-course will be correlated with the time-course of activity measured at every voxel in the brain to yield a whole-brain map of r-values. The r-values will be transformed to Gaussian variables via Fisher’s transform. The resulting seed region connectivity maps for each In-Magnet Assessment of each subject will be entered into group-level analyses after transformation to common space (see above section ii.).

B. R61 Phase:

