- i. *To determine if NF increases control over amygdala more than sham feedback:* Activation in the target region of the amygdala in the down-regulate blocks (computed as described in above section A.iv.) will be compared across groups to see if mean activation is larger in the NF group than the sham feedback group, with an effect size of the group difference $d > 1$. If so, this will satisfy “Go” criteria and the study will proceed to the R61 phase. If not, the decision will be “No Go”.

C. R33 Phase:

- i. *To determine if NF increases control over the amygdala significantly more than sham feedback:* Activation in the amygdala in the down-regulate blocks (computed as described in above section A.iv.) will be entered into a 2x2 ANOVA with factors time-point (2 levels: pre and post) and group (2 levels: NF and sham). If there is a significant interaction of group by time-point at a $p < 0.05$ level, a two-sample t-test will be used to see if the improvement in control was greater in the NF subjects than the sham subjects.

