- ii. *To determine if NF improves symptoms more than sham feedback and to correlate symptom changes with control over the amygdala:* A 2x2 ANOVA with factors group (2 levels: NF and sham) and time-point (2 levels: pre-intervention and first post-intervention) will be run on the past-month scores from the clinician-administered symptom checklist collected during the Full Clinical Assessment sessions. If there is a significant group-by-time-point interaction and post-hoc t-tests reveal a significantly greater improvement in symptoms in the NF group than the sham group, we will conclude the NF does improve clinical symptoms more than the sham. The change in score will also be correlated across NF subjects with the change in control over the brain area (computed as described above in section A.iv.). We hypothesize a decrease in score (indicating improvement in PTSD symptoms) will be correlated with an increase in control. A secondary analysis will be run using all 3 time points of scores collected (pre, 1 month post, and 2 month post intervention) to explore the long-term clinical effects. A linear mixed model analysis with group (NF or sham) by time-point (pre, 1 month post, and 2 month post intervention) will be used to capture the longitudinal effect of the clinical intervention. Finally, if the intervention does appear to reduce symptoms, we will explore whether these changes are greatest for scores on PTSD criterion B (intrusion) and criterion E (alteration in arousal reactivity) as these are expected to be most closely related to successful amygdala regulation.

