- iii. *To determine if NF changes resting connectivity to the amygdala and if these changes are correlated with symptom improvement and improved ability to regulate the amygdala:* After transforming the resting connectivity maps to the reference space (see above section A.v.), we will subtract the seed region connectivity map of the resting data collected pre-intervention from that collected in the post-intervention to yield a map of change in amygdala connectivity for each subject. Two-sample voxel-wise t-tests will be computed across subjects comparing these maps in the NF and sham groups. The resulting group difference map will be cluster corrected, using a non-parametric permutation test to identify those areas of the brain “rewired” by NF. For each locus surviving cluster correction, we will also examine whether the change in amygdala connectivity in this locus for each NF subject is correlated with their symptom improvement or their improvement in control over the amygdala.

SECTION II: RESEARCH INVOLVING DRUGS, BIOLOGICS, RADIOTRACERS, PLACEBOS AND DEVICES

If this section (or one of its parts, A or B) is not applicable, check off N/A and delete the rest of the section.

A. RADIOTRACERS N/A

B. DEVICES N/A

1. Are there any investigational devices used or investigational procedures performed at Yale-New Haven Hospital (YNHH) (e.g., in the YNHH Operating Room or YNHH Heart and Vascular Center)? Yes No

SECTION III: RECRUITMENT/CONSENT AND ASSENT PROCEDURES

1. Targeted Enrollment: Give the number of subjects...

a. Targeted for enrollment at Yale for this protocol: 60
 b. If this is a multi-site study, give the total number of subjects targeted across all sites: 60

2. Indicate recruitment methods below. Attach copies of any recruitment materials that will be used.

 Flyers	 Internet/web postings	 Radio
 Posters	 Mass email solicitation	 Telephone
 Letter	 Departmental/Center website	 Television
 Medical record review*	 Departmental/Center research boards	 Newspaper

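### Both R33 group comparisons reduce to t-tests on change scores; adjusting for the baselines already collected would usually be more precise at almost no cost

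*Combined protocol and SAP*

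**What the plan says.** Section I, item 13.C sets out two group comparisons for the R33 phase.

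- **Amygdala control (13.C.i).** Down-regulate activation "will be entered into a 2x2 ANOVA with factors time-point (2 levels: pre and post) and group (2 levels: NF and sham". If the interaction reaches p < 0.05, "a two-sample t-test will be used to see if the improvement in control was greater in the NF subjects than the sham subjects".
- **Symptoms (13.C.ii).** "A 2x2 ANOVA with factors group (2 levels: NF and sham) and time-point (2 levels: pre-intervention and first post-intervention) will be run" on the past-month clinician-administered scores. A significant interaction, with post-hoc t-tests favouring NF, leads to the conclusion that NF improves symptoms more than sham.

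A secondary symptom analysis is also planned: "A linear mixed model analysis with group (NF or sham) by time-point (pre, 1 month post, and 2 month post intervention) will be used". It lists the pre-intervention score as one of the outcome time-points. The plan does not say whether the groups share a baseline mean, or what covariance structure is used.

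Item 13 names no baseline covariate. Both baselines precede allocation. CAPS-5 establishes the diagnosis at the Initial Clinical Assessment. At In-Magnet Assessment 1, "Functional resting state data will be collected, as well as four control runs". After that, "All subjects who remain eligible following the localizer will be randomized to receive either NF or sham feedback".

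On size, Section III, item 1 gives only this: "Targeted for enrollment at Yale for this protocol: 60". There is no power calculation, and the split between the R61 and R33 phases is not stated.

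**The concern.** Each subject contributes one pre and one post value to each test. A 2x2 interaction on such data compares mean change between arms, so the follow-up t-test on improvement repeats the same test and adds only the direction.

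A change score fixes the slope of post on pre at 1. When the pre/post correlation is moderate and the SDs are similar, the best slope is below 1, and subtracting the whole baseline adds noise to the comparison. Estimating the slope from the data removes that noise.

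The issue is lost efficiency, not bias. It matters because the efficacy conclusion for symptoms is tied explicitly to one of these tests, the R33 conclusion on control rests on the other, and the trial is small.

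**Working it through.** **Inputs.** Sixty is the enrolment target for the whole protocol, and subjects without an amygdala target leave before randomisation, so 30 per arm is an upper bound. The plan requires at least as many NF as sham subjects and states no ratio; 1:1 is assumed. The plan gives p < 0.05 for control and no level for symptoms; two-sided 0.05 is assumed for both. The pre/post correlation rho, the SDs and the R33 effect are not given. I use rho from 0.3 to 0.9 and an effect of 0.6 SD, both assumptions. The d > 1 threshold in item 13.B is the R61 go criterion and is not used here. The plan has no power figure to reproduce.

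**Step 1: the identity.** With n subjects per arm, let L be the difference between arms in mean change and s² the pooled variance of change.

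- Interaction sum of squares (1 df) = nL²/4.
- Within-subject error mean square = s²/2.
- F = (nL²/4)/(s²/2) = nL²/(2s²).
- Two-sample t on change: t² = L²/(2s²/n) = nL²/(2s²).

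The two are equal. On simulated data F and t² were both 5.8418 at 30/30 and both 0.2045 at 32/28. The identity needs time-point to be within-subject, which the t-test on improvement implies but the plan does not state. Run as a between-subject two-way ANOVA, the first example gave F = 3.16.

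**Step 2: variances, equal SDs (SD = 1).** Per-subject variance is:

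- change score: 2(1 − rho);
- ANCOVA: (1 − rho²)(1 + 1/(N − 4)), where the last factor is the average cost of chance baseline imbalance (1 + 1/56 = 1.018 at N = 60).

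**Step 3: power.** Noncentral t with noncentrality 0.6/√(variance × 2/30), on 58 df (change score) or 57 df (ANCOVA). At rho 0.5 the noncentralities are 0.6/√(1.00/15) = 2.32 and 0.6/√(0.763/15) = 2.66.

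| rho | Change-score variance | ANCOVA variance | Ratio | Power, change score | Power, ANCOVA |
|---|---|---|---|---|---|
| 0.3 | 1.40 | 0.926 | 0.662 | 49% | 66% |
| 0.5 | 1.00 | 0.763 | 0.763 | 63% | 74% |
| 0.7 | 0.60 | 0.519 | 0.865 | 84% | 89% |
| 0.9 | 0.20 | 0.193 | 0.967 | 99.9% | 99.9% |

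The smallest effect detectable with 80% power falls from 0.87 to 0.71 SD (rho 0.3), 0.74 to 0.64 (0.5) and 0.57 to 0.53 (0.7). At 20 per arm, power for 0.6 SD goes from 35% to 48%, 46% to 56% and 67% to 72% at rho 0.3, 0.5 and 0.7. Simulation of 20,000 trials per scenario at 30 per arm agreed, with null rejection between 4.7% and 5.3% for both methods.

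**Step 4: unequal SDs.** With post SD = k × pre SD, the ratio is k²(1 − rho²)/(k² + 1 − 2·rho·k), times 1.018 at N = 60.

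| k | rho 0.3 | rho 0.5 | rho 0.7 |
|---|---|---|---|
| 1.25 | 0.798 | 0.909 | 0.998 |
| 1.5 | 0.887 | 0.982 | 1.016 |

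Before the 1.018 factor the ratio never exceeds 1, and it reaches 1 only when the slope of post on pre is 1. The most that can be lost on average is therefore the factor itself: 1/56 = 1.8% at N = 60, 1/36 = 2.8% at N = 40, 1/16 = 6.3% at N = 20. With equal SDs, ANCOVA loses only if rho exceeds about 0.96 (N = 60) or 0.95 (N = 40).

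**Step 5: the planned mixed model.** A generalised least squares check used three visits, complete data, equal SDs and the same rho between all visits. If each arm keeps its own baseline mean, the 1-month contrast has 1.000 times the change-score variance. If the arms share a baseline mean, the ratio is 0.65, 0.75, 0.85 and 0.95 at rho 0.3, 0.5, 0.7 and 0.9, before the small imbalance cost.

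**The case against.** The strongest reply is that nothing here is an error: both analyses validly estimate the same group difference, and the documents do not show how large the benefit would be. That is correct, and it is why this is a recommendation on efficiency.

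Several narrower points also stand.

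- **Equal SDs flatter the gain for CAPS-5.** Because CAPS-5 establishes eligibility, baseline scores may have a narrower spread than later ones. At a post/pre SD ratio of 1.25 and rho 0.7, the variance ratio is 0.998 and nothing is gained. The power figures above should not be read as a forecast for symptoms.
- **The 2% worst case is specific to N = 60.** It is larger in a smaller R33 sample, as step 4 shows.
- **A low correlation for the amygdala measure is a judgement.** The measure draws on few data: four control runs per session, and "All analyses outlined in the following sections will use data from the regulation blocks of the untrained traumas unless otherwise noted". No reliability figure is given.
- **At low rho, most of the gain comes from not subtracting a noisy baseline.** At rho 0.3 a post-only comparison has variance 1.00, so (1.40 − 1.00)/(1.40 − 0.926) = 84% of the improvement comes from that alone.
- **The mixed model is under-specified, so it might be fitted with a common baseline mean.** The plan does not say so, and the model is secondary in any case.
- **Timing matters.** Subjects are unblinded individually after their final assessment, and an R61 group comparison precedes R33, so a late change of test could look data-driven.

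These points limit the size of the benefit and how it may be claimed. They do not reverse the direction: the average loss is bounded at a few per cent, while the variance reduction can reach about a third.

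**Conclusion.** The concern holds. Read as within-subject analyses, both R33 ANOVAs are change-score t-tests with no baseline adjustment, although both baselines are available before randomisation. With equal SDs and 30 per arm, adjustment cuts variance by about 34%, 24%, 13% and 3% at rho 0.3, 0.5, 0.7 and 0.9. At rho 0.5 the 60 subjects would count as about 79 (60/0.763) under the planned test. The gain shrinks, and can become a loss of about 2% at N = 60, if the post SD is well above the pre SD. The direction and the bound on the loss are firm; the realised gain depends on a correlation and SDs that the documents do not give. The planned tests remain valid, so this is an improvement the plan should make rather than a flaw that invalidates it.

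**What to change.** Replace each ANOVA-then-t sequence with one pre-specified estimate and its 95% CI:

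- **Symptoms:** 1-month CAPS-5 regressed on group and baseline CAPS-5; report the adjusted NF-sham difference.
- **Control:** post-intervention down-regulate beta (untrained traumas) regressed on group and the pre-intervention beta; report the adjusted NF-sham difference.

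For CAPS-5 the deciding estimate may instead be the 1-month contrast from the mixed model already planned, provided the SAP states a baseline mean common to both arms and an unstructured covariance. That version also retains a subject who misses month 1 but returns at month 2.

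Date the change before any R33 outcome is compared by arm, and keep the change-score t-test as a sensitivity analysis. State the significance level and sidedness for both outcomes.

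The cost is SAP wording, one degree of freedom, and on average about 1.8% of variance at N = 60 (2.8% at N = 40). No new data or visits are needed.
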